## 5.5 Withdrawal Criteria (if applicable)

Should a subject wish to stop treatment in the trial or if an investigating physician decides to withdraw a subject from the trial due to side effects, incompliance or for other reasons, he/she needs to inform the CRO as soon as possible.

Withdrawn subjects will not be replaced.

# 6 STUDY PARAMETERS

## 6.1 Efficacy Measures

### 6.1.1 Primary Efficacy Variable(s)

Mean change in ETDRS BCVA at Week 12 compared to baseline.

### 6.1.2 Secondary Efficacy Variable(s)

Mean change in ETDRS BCVA letters at Weeks 2, 4, 8, and 16 compared to baseline;

Mean ETDRS BCVA letters at Weeks 2, 4, 8, 12, and 16:

Percent of patients who gain  $\geq 10$  or  $\geq 15$  ETDRS letters at week 12 compared to baseline;

Percent of patients who lose  $\geq 15$  ETDRS letters or more at week 12 compared to baseline;

Mean change in central macular thickness (CMT) as assessed by SD-OCT at Weeks 2, 4, 8, 12, and 16 compared to baseline;

Mean CMT as assessed by SD-OCT at Weeks 2, 4, 8, 12, and 16;

Quality of life as assessed by NEI VFQ-25 at baseline and week 12

## 6.2 Safety Measures

Subjects will be monitored for safety on all study visits.

### Adverse Events

Safety Laboratory Tests: Biochemistry and Hematology

Slit Lamp Examination Parameters indicating ocular toxicity to the investigational drug

Intraocular Pressure

Dilated Indirect Ophthalmoscopy

### **6.3 Other Measures**

At baseline and week 12 blood samples will be drawn for measurements of HbA1c, haematology and chemistry.

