## **2 STUDY OBJECTIVES**

1. Compare the effects of DexNP eye drops and eye drops containing vehicle on visual acuity and central macular thickness in patients with DME over 12 weeks.
2. Monitor safety of the DexNP eye drop suspension treatment over 12 weeks.

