## 4 OVERALL STUDY DESIGN

Multi-center

Double-masked

Parallel group

Randomized (2: 1; active: vehicle)

Vehicle controlled

Prospective

12 weeks active treatment, 4 weeks safety follow-up without treatment

1 drop three times a day

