  - u) Have a history of prior IVT, subtenon, or periocular, non-sustained release, steroid therapy within 3 months prior to Visit 1 in the study eye (e.g., triamcinolone)
  - v) Have a history of intravitreal sustained release dexamethasone therapy within six months prior to Visit 1 in the study eye;
  - w) Have a history of intravitreal sustained release fluocinolone within three years prior to Visit 1 in the study eye;

- x) Have a history of prior treatment of intravitreal (IVT) aflibercept within 8 weeks and ranibizumab/bevacizumab within 6 weeks of Visit 1 in the study eye;
- y) Have a history of prior treatment for DME with any other (than previously listed) approved treatment which is not labeled for DME within one year prior to Visit 1 in the study eye;
- z) Have high-risk proliferative diabetic retinopathy (PDR), defined in the ETDRS study as at least one of the following:
  - New vessels within one disc diameter of the optic disc (NVD)  $\geq$  1/3 disc area;
  - Any NVD with vitreous or pre-retinal hemorrhage;
  - New vessels elsewhere in the retina (NVE)  $\geq$  1/2 disc area and pre-retinal or vitreous hemorrhage;
- aa) Have uncontrolled ocular hypertension or glaucoma in either eye, defined as intraocular pressure (IOP)  $\geq$  22 mmHg on more than 1 IOP lowering medications at Visit 1
- bb) Have poor media clarity, pupillary constriction (i.e., senile miosis), or lack cooperation that, in the opinion of the evaluating Investigator, would interfere with any study procedures, evaluations, or interpretation of data
- cc) Have any ocular condition that, in the opinion of the Investigator, may require intervention, interfere with evaluations of efficacy or safety or interpretation of data collected in the study
- dd) Have an estimated Glomerular Filtration Rate (eGFR) of  $<$  15mL/min/1.73m^2 as per CKD-EPI equation at Visit 1
- ee) Have a systolic blood pressure  $<$  90 or  $>$  160 mmHg and / or a diastolic blood pressure  $>$  100 mmHg at Visit 1 and 2
- ff) Have a known or suspected hypersensitivity to any components of the test agent
- gg) Be a female subject who is pregnant or lactating or has a positive pregnancy test at Visit 1 or has been pregnant within 6 months before Visit 1 or breast-feeding within 3 months before Visit 1, or planning to become pregnant within 9 months from Visit 1

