## 8.4 Schedule of Visits, Measurements and Dosing

### 8.4.1 Scheduled Visits

Refer to Appendix 1 for a schedule of visits and measurements.

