### **10.3 Sample Size**

Assuming a difference in the mean change from baseline ETDRS BCVA to Week 12 of 3.5 letters between DexNP and vehicle, a common standard deviation in the change from baseline ETDRS BCVA letters to Week 12 of 8 letters within each treatment group, an overall 1-sided alpha = 0.15, a 2:1 randomization, and an interim analysis when 50% of the subjects complete Week 12 using an O'Brien-Fleming alpha spending function, 58 DexNP and 29 Vehicle subjects (study eyes) are required to have 80% power to reject the null hypothesis. Assuming 10% discontinuation rate, a total of 96 subjects will be randomized.

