## **Appendix 1: Schedule of Visits and Measurements**

### Schedule of Visits and Measurements

#### **7 visits over the course of 16 weeks:**

##### Study visit schedule

- Screening Visit (Day -1 to -28)
- Baseline (Day 1)
- Week 2
- Week 4
- Week 8
- Week 12 - Primary end point
- Week 16 - final visit

(visit window is  $\pm$  3 days)

	Visit 1	Visit 2	Visit 3	Visit 4	Visit 5	Visit 6	Visit 7
Procedure	Screening	Day 1	Week 2	Week 4	Week 8	Week 12	Week 16
Informed Consent	X						
Randomisation		X					
Demographic Data		X					
Medical and Ophthalmology History	X	X					
Medication History and Update	X	X	X	X	X	X	X
Visual Acuity	X	X	X	X	X	X	X
Biomicroscopy	X	X	X	X	X	X	X
IOP	X	X	X	X	X	X	X
Ophthalmoscopy	X	X				X	X
OCT	X	X	X	X	X	X	X
Cataract evaluation		X				X	
Blood test	X						X
Blood pressure	X	X	X	X	X	X	X
Urine pregnancy test	X*						
VFQ-25		X				X	
Investigational Product Dispensed		X		X	X		
Investigational Product Returned				X	X	X	
Adverse Events		X	X	X	X	X	X
Exit from Study							X

\*if applicable

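### Section 6.3 takes the follow-up blood sample at Week 12 and Appendix 1 takes it at Week 16; under Appendix 1 no laboratory sample is scheduled on treatment

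*Combined protocol and SAP*

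**What the plan says.** Section 6.3 (Other Measures) sets the laboratory sampling times: "At baseline and week 12 blood samples will be drawn for measurements of HbA1c, haematology and chemistry". It then lists the haematology and chemistry panels.

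Section 8.4.1 sends the reader elsewhere for timing: "Refer to Appendix 1 for a schedule of visits and measurements". In the Appendix 1 table, the blood test row has two marks, at Visit 1 (Screening) and Visit 7 (Week 16). Visits 2 to 6 are blank.

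Section 4 describes the periods as "12 weeks active treatment, 4 weeks safety follow-up without treatment". The second study objective in Section 2 is: "Monitor safety of the DexNP eye drop suspension treatment over 12 weeks".

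Section 10.1.3 lists laboratory tests among the safety endpoints. Section 10.6.5 plans continuous summaries of them by visit, with change from baseline, but does not name the visits.

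**The concern.** Both texts are current protocol text, and they place the only follow-up sample on opposite sides of the end of treatment. Section 6.3 puts it at the Week 12 visit, which closes the treatment period. Appendix 1 puts it at the exit visit, after the four weeks without treatment.

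A site working from the visit table would draw no blood between the start and the end of treatment. The laboratory change from baseline would then compare a pre-treatment value with an off-treatment value. A laboratory effect that reverses once the drops are stopped could go unseen, although the objective concerns safety during the 12 weeks of treatment. A missed Week 12 sample cannot be recovered later.

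**Working it through.** **Step 1. Is the Appendix 1 row read correctly?** The table was extracted from a PDF, so the column positions were checked against other rows:

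- The VFQ-25 row has marks at Day 1 and Week 12, which agrees with Section 8.3.1.
- The row "Investigational Product Returned" has its last mark at Visit 6 (Week 12), and no product is dispensed at that visit. This agrees with 12 weeks of treatment.
- The study exit row has its only mark in the Week 16 column. The second blood test mark is in that same column.

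The Week 16 mark is therefore not an extraction fault.

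**Step 2. The two schedules side by side.**

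| Visit | Section 6.3 | Appendix 1 |
|---|---|---|
| Visit 1, Screening | – | blood |
| Visit 2, Day 1 | blood (baseline) | – |
| Visit 3, Week 2 | – | – |
| Visit 4, Week 4 | – | – |
| Visit 5, Week 8 | – | – |
| Visit 6, Week 12 | blood | – |
| Visit 7, Week 16 | – | blood |

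Of the four post-baseline visits up to Week 12 (Visits 3 to 6), Section 6.3 samples at 1 and Appendix 1 at 0.

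**Step 3. How far off treatment is the Appendix 1 sample?** Week 12 is 84 days and Week 16 is 112 days; each visit has a window of ±3 days.

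- Nominal interval: 112 − 84 = 28 days.
- Shortest: (112 − 3) − (84 + 3) = 109 − 87 = 22 days.
- Longest: (112 + 3) − (84 − 3) = 115 − 81 = 34 days.

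These are intervals from the Week 12 visit. For a subject who stopped the drops earlier, the time off treatment is longer.

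**Step 4. Does another passage settle the conflict?**

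- Section 6.2 says "Subjects will be monitored for safety on all study visits" and lists laboratory tests among the safety measures, but names no sampling visit. Neither Section 6.3 nor Appendix 1 samples at every visit.
- Section 8.3.1 lists the examinations at study visits and includes no blood draw.
- Section 8.4.2 allows unscheduled visits but attaches no laboratory sample to them.
- Section 10.6.5 summarises whatever visits have data and does not define them.

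No passage gives precedence to either text.

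**Step 5. Does the baseline half of the mismatch matter?** Section 6.3 says baseline and Appendix 1 says Screening. Blood is needed at Visit 1 in any case, because HbA1c (Section 5.3) and eGFR (Section 5.4, "as per CKD-EPI equation at Visit 1") decide eligibility. Section 10.6.1 defines baseline as the last available value before treatment starts, so the Visit 1 sample qualifies. This half is harmless.

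**The case against.** The strongest reply is that little depends on this sample. Laboratory data are summarised descriptively, with no test. Even Section 6.3 provides only one on-treatment sample, at the very end. The earlier randomised DexNP trial in DME, described in Section 1, reports HbA1c as unaffected. The laboratory change it does report is in serum cortisol, which is not in this trial's panel, so a Week 12 draw would not capture it. The case report form, the monitoring plan or the optional study manual might also fix one sampling visit for all sites, and none of these is available here. All of this stands, and it limits the size of the point. It does not remove the contradiction: an unseen operational document cannot show that the protocol is consistent.

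A reader might infer more in three directions, and the documents do not support them.

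- *That sites will split between the two texts and reduce the Week 12 laboratory data to some fraction of subjects.* A split is possible with about 13 sites, but the documents give no share and no evidence of one. Section 10.3 says "58 DexNP and 29 Vehicle subjects (study eyes) are required to have 80% power to reject the null hypothesis", but those are efficacy-power numbers and would be the wrong denominators here. The safety population in Section 10.5 is every randomised subject who receives at least one dose, so up to 64 and 32.
- *That the loss can be expressed as an upper confidence limit on the rate of some abnormality.* Section 10.6.5 plans continuous summaries for laboratory data. It plans no abnormality rate; proportions above a threshold are planned for IOP only.
- *That a known laboratory effect would be missed.* In the earlier trial, cortisol on DexNP was 9.7 at baseline. It was lower by 5.5 at 4 weeks, 5.0 at 8 weeks, 2.5 at 12 weeks and 0.4 at 16 weeks, four weeks after the drops ended. This shows that an on-treatment effect can have nearly gone by the time Appendix 1 samples. The dosing frequency was stepped down in that trial, so part of the recovery came before stopping. It does not show that any analyte in the present panel changes on treatment.

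**Conclusion.** The point holds. Section 6.3 and Appendix 1 contradict each other on the follow-up blood sample, and neither is given precedence. Where Appendix 1 is followed, a listed safety endpoint has 0 of 4 possible samples in the treatment period, against 1 of 4 under Section 6.3. Its only follow-up value is taken nominally 28 days after the Week 12 visit (22 to 34 with the windows). The laboratory change from baseline would then not describe the period named in objective 2.

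The effect is limited. The endpoint is descriptive, and the primary efficacy analysis does not use it. Adverse events, IOP, biomicroscopy and blood pressure are marked in Appendix 1 at every visit from Week 2 to Week 12. It should be fixed, but it does not threaten the trial's main conclusion.

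The conclusion rests on the column positions in Appendix 1, which agree with three other rows, and on Week 12 being the end of treatment, which Section 4 and the product-return row both support. It needs no assumption about how sites behave.

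**What to change.** Reconcile Section 6.3 and Appendix 1 so that the laboratory safety endpoint has a sample in the treatment period. One way is to mark the blood test at Visit 6 in Appendix 1, which matches the Week 12 time already in Section 6.3.

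State whether the Week 16 sample is kept. If it is, add Week 16 to Section 6.3 and have Section 10.6.5 report that value as post-treatment. No separate statement on the laboratory baseline is needed, because Section 10.6.1 covers it.

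The cost is one mark in the Appendix 1 row, plus a clause in Section 6.3 and one in Section 10.6.5 if Week 16 is kept. Counting the Visit 1 sample as baseline, moving the mark from Week 16 to Week 12 leaves two draws per subject. Keeping both makes three, that is 2 + 1, with the extra draw at a visit that already takes place.

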#### **Clinical trial #2: DME (Ohira et al. 2015): 12 patients treated with DexNP**

This clinical trial (Ohira et al. 2015) was a randomized, controlled trial topical 1.5% dexamethasone  $\gamma$ -cyclodextrin nanoparticle eye drops (DexNP) vs. posterior subtenon injection of triamcinolone acetonide in diabetic macular oedema (DME). This trial ran for 16 weeks with DexNP applied for 12 weeks.

In this prospective, randomized, controlled trial, 22 eyes of 22 consecutive patients with DME were randomized to (i) topical treatment with DexNP  $\times$ 3/day (weeks 1-4),  $\times$ 2/day (weeks 5-8) and  $\times$ 1/day (weeks 9-12) and no eye drops weeks 13-16 or (ii) one posterior subtenon injection of 20 mg triamcinolone acetonide. Study visits were at baseline and 4, 8, 12 and 16 weeks.

The logMAR (Snellen) visual acuity (mean  $\pm$  SD) improved significantly with DexNP from 0.41  $\pm$  0.3 (Snellen 0.39) to 0.32  $\pm$  0.25 (0.48) and 0.30  $\pm$  0.26 (0.50) at 4 and 8 weeks, respectively. One-third of the DexNP group improved more than 0.3 logMAR units. For triamcinolone, logMAR changed significantly from 0.42  $\pm$  0.28 (0.38) at baseline to 0.32  $\pm$  0.29 (0.48) at 4w and 0.33  $\pm$  0.37 (0.47) at 12w. The central macular thickness (CMT) decreased significantly with DexNP from 483  $\pm$  141  $\mu$ m to 384  $\pm$  142  $\mu$ m at 4w and 342  $\pm$  114  $\mu$ m at 8w (Figure 1). For triamcinolone, CMT decreased significantly at all time-points: 494  $\pm$  94  $\mu$ m, 388  $\pm$  120, 388  $\pm$  145, 390  $\pm$  136 and 411  $\pm$  104  $\mu$ m at 0, 4, 8, 12 and 16 weeks, respectively.

[figure not shown]

[figure not shown]
[figure not shown]
Figure 1: OCT images at baseline and after 4 weeks of DexNP TID in an eye with DME (Ohira et al. 2016)

There was a modest increase in intraocular pressure (IOP) at all time-points with DexNP while no increase was seen with triamcinolone. IOP was  $14 \pm 4$  mmHg at baseline and rose an average of  $5 \pm 6$  mmHg at 4 weeks,  $6 \pm 7$  mmHg at 8 weeks and  $7 \pm 7$  mmHg at 12 weeks. IOP returned to normal and was  $1 \pm 6$  mmHg higher than baseline at 16 weeks, i.e. 4 weeks after DexNP treatment was stopped.

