Serum cortisol was mildly affected by both treatments. With DexNP Cortisol was  $9.7 \pm 3.7$  at baseline and fell by  $5.5 \pm 5.1$  at 4 weeks,  $5.0 \pm 4.2$  at 8 weeks,  $2.5 \pm 4.5$  at 12 weeks and  $0.4 \pm 2.5$  at 16 weeks. Cortisol changed also in the triamcinolone injected group and the change was sustained longer. Here it was  $14.2 \pm 4.5$  at baseline and fell by  $3.1 \pm 2.2$  at 4 weeks,  $3.8 \pm 4.8$  at 8 weeks,  $2.8 \pm 3.3$  at 12 weeks and  $3.5 \pm 5.3$  at 16 weeks.

HbA1c was unaffected. It was  $7.05 \pm 1.08$  % at baseline and rose by  $0.19 \pm 0.80$  % at 12 weeks. The triamcinolone group was similar.

Topical DexNP significantly improve visual acuity and decrease macular thickness in patients with DME (Figure 2). The effect is similar to that of subtenon triamcinolone and that of ranibizumab (using indirect comparison with published data). A modest increase in IOP was seen with the nanoparticle eye drops, but IOP normalized after the discontinuation of treatment.

Legend:  
Ranibizumab - RESTORE (n=115)      Ranibizumab - RESOLVE (n=102)  
Laser - RESTORE (n=110)      Triamcinolone (n=10)  
DexNP - Ohira (n=12)      DexNP - Tanito (n=19)

Figure 2: The data on visual acuity (above) and central retinal thickness (below) is compared between two DexNP studies (in colour; see colour code above) and ranibizumab clinical trials (gray). Ohira et al. 2015; Tanito et al. 2011; Massin et al. 2010 (RESOLVE); Mitchell et al. 2011 (RESTORE)

Diabetic macular edema may be treated with topical eye drops. The dexamethasone-cyclodextrin nanoparticle eye drops significantly reduce retinal thickness and improve visual acuity in diabetic macular edema.

Other studies on eye drops for macular edema:

Earlier studies have suggested that macular edema may be treated with topical eye drops with other drug molecules. Campochiaro et al. showed that administration of topical mecamylamine, a nonspecific nicotinic acetylcholine receptor blocker, has positive effects in patients with diabetic macular edema. (Campochiaro et al. 2010) Genead and Fishman reported that topical therapy with dorzolamide hydrochloride 2%, improved visual acuity and macular edema in patients with retinitis pigmentosa and Usher syndrome.

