### 8.2 Concurrent Therapies

The use of any concurrent medication, prescription or over-the-counter, is to be recorded on the subject's source document and corresponding case report form (CRF) along with the reason the medication was taken.

Concurrent use of other eye drops is not allowed. Should concurrent treatment with IOP lowering eye drops (prefer prostaglandin) become necessary due to increased IOP, those eye drops should be administered in the evening 15 minutes before DexNP/Vehicle eye drops.

Other treatments for DME are not allowed in the study eye while the patients are included in the study except if they meet the rescue criteria as described in 8.2.2 below.

If the fellow eye needs any treatment for DME or any other conditions, standard of care (i.e. anti-VEGF for DME) can be applied except steroids. So i.e. Ozurdex or topical dexamethasone will not be allowed for the treatment of the fellow eye during the course of the study.

The use of contact lenses is NOT allowed during the active study treatment phase of 12 weeks.

Concurrent enrollment in another investigational drug or medical device study is not permitted.

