## 10.6 Statistical Analysis

### 10.6.1 Methods of Analysis

Summaries for continuous variables will include the sample size, mean, standard deviation, median, minimum, and maximum. Summaries for discrete variables will include frequencies and percentages. Differences between treatment groups will be calculated as DexNP – Vehicle and change from baseline will be calculated as follow-up visit – baseline. The baseline visit will be defined as the last non-missing measure prior to initiation of investigational treatment. All efficacy analyses will use a one-sided alpha = 0.15 test unless otherwise stated.

All summaries will be presented by treatment group and where appropriate by visit.

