#### 10.6.5 Safety Analyses

All safety analyses will be performed on the safety population. The primary safety analysis will summarize ocular and non-ocular treatment-emergent AEs (TEAEs) using discrete summaries at the subject level by system organ class and preferred term for each treatment group. Ocular TEAEs will be summarized separately for all study and fellow eyes. A TEAE will be defined as occurring after the first dose of study medication. Serious adverse events and treatment-related ocular and non-ocular TEAEs will be summarized similarly. Ocular and non-ocular TEAEs will also be summarized by severity.

Slit lamp biomicroscopy and dilated indirect ophthalmoscopy measures will be summarized at each visit using discrete summary statistics.

Intraocular pressure will be summarized at each visit, using continuous and discrete summary statistics, including change from baseline and the proportion of study eyes with an increase from baseline in IOP of 10 mmHg or more and the proportion of study eyes with IOP of 30 mmHg or more.

Safety laboratory data will be summarized at each visit, using continuous summary statistics, including change from baseline.

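### Section 6.3 puts the post-baseline safety bloods at Week 12, but Appendix 1 schedules them at Week 16, about four weeks off drug, and nothing says which governs

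*Combined protocol and SAP*

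**What the plan says.** Section 6.3 (Other Measures) gives both the timing and the content of the laboratory sampling: "At baseline and week 12 blood samples will be drawn for measurements of HbA1c, haematology and chemistry". The haematology and chemistry analytes are listed directly beneath.

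Section 8.4.1 does not repeat this timing. It says only: "Refer to Appendix 1 for a schedule of visits and measurements". Appendix 1 has one row for blood tests. It carries a mark under Visit 1 (Screening) and under Visit 7 (Week 16), and is blank at Day 1 and at Weeks 2, 4, 8 and 12.

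Section 4 describes the design as "12 weeks active treatment, 4 weeks safety follow-up without treatment", so Week 16 is an off-treatment visit.

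Three other places depend on these samples:

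- Section 2, Objective 2, is to monitor the safety of DexNP over the 12 weeks.
- Section 10.1.3 lists biochemistry and haematology among the safety endpoints.
- Section 10.6.5 plans the analysis: "Safety laboratory data will be summarized at each visit, using continuous summary statistics, including change from baseline".

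For the starting value, Section 10.6.1 says: "The baseline visit will be defined as the last non-missing measure prior to initiation of investigational treatment".

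**The concern.** Two parts of one protocol give different times for the only planned post-baseline blood sample. One falls at the end of treatment and the other at the end of the washout. The choice decides what the laboratory safety data can say. A Week 12 sample describes patients on the drug; a Week 16 sample describes patients who have been off it for about a month.

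Sites and monitors commonly work from the visit schedule, and here 8.4.1 refers them to it. If all sites follow it, the trial of a steroid in patients with diabetes has no planned glucose, HbA1c, chemistry or haematology result during exposure. If some of the roughly 13 sites follow 6.3 and others follow Appendix 1, the by-visit laboratory summary will hold Week 12 results from some sites and Week 16 results from others, with neither complete. A Week 12 sample that was not taken cannot be recovered afterwards.

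**Working it through.** The plan gives no figure to reproduce. The check compares the texts and counts days and samples.

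**1. Is the Appendix 1 row read correctly?** The column order is Screening, Day 1, Week 2, Week 4, Week 8, Week 12, Week 16. The blood-test row has a mark, five blanks and a mark, so the marks sit in columns 1 and 7. Other rows test the alignment:

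| Row in Appendix 1 | Where marked | Agrees with |
|---|---|---|
| VFQ-25 | Day 1, Week 12 | Section 8.3.1 |
| Randomisation | Visit 2 (Day 1) | Section 8.1.5 |
| Exit from study | Week 16 | Section 8.8 (16-week duration) |

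These rows fall where the body text puts them, so a shifted cell is unlikely.

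**2. Does any text settle the conflict?** Section 8.3.1, which lists the procedures at each visit, does not mention blood tests. Section 15 has a precedence rule, but it ranks the trial agreement above the protocol, not one protocol section above another. Nothing else bears on it.

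**3. How far off drug is the Week 16 sample?** Inputs: Week 12 = day 84 and Week 16 = day 112 after the start of treatment; ±3 days at each visit (Appendix 1). Assumption: the last drop is taken at the Week 12 visit.

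- Nominal: 112 − 84 = 28 days
- Shortest: (112 − 3) − (84 + 3) = 109 − 87 = 22 days
- Longest: (112 + 3) − (84 − 3) = 115 − 81 = 34 days

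A patient who stops the drops early is off drug for longer.

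**4. How many scheduled on-treatment samples result?**

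| Text followed | Post-baseline draw | Per patient on treatment | Whole trial |
|---|---|---|---|
| Section 6.3 | Week 12 | 1 | up to 96; 58 + 29 = 87 on the discontinuation rate assumed in Section 10.3 |
| Appendix 1 | Week 16 | 0 | 0 |

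**5. What does Section 10.6.5 then deliver?** Under 6.3, the laboratory change is from the last pre-treatment value to Week 12, on drug. Under Appendix 1, the same pre-treatment value is compared only with Week 16, off drug.

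**6. Is the baseline half also a conflict?** Not one of substance. Section 6.3 says baseline and Appendix 1 marks screening. Section 10.6.1 takes the last value before treatment, so the Visit 1 sample qualifies. That draw is needed in any case, because the HbA1c limit (Section 5.3) and the eGFR limit (Section 5.4) are both applied at Visit 1.

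**The case against.** The strongest reply is that the intended design is plain and the schedule contains a slip. Appendix 1 says only that a blood test is done; the analytes appear in 6.3, directly below the sentence naming Week 12. A site must open 6.3 to know what to order and will probably see the timing there. Unscheduled visits (8.4.2) can also yield on-treatment results. All of this stands as mitigation. It makes zero on-treatment samples a worst case that applies to scheduled samples only. It does not remove the conflict, because 8.4.1 refers sites to the appendix for timing and no unscheduled draw is planned.

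Two stronger readings are tempting, and the documents support neither.

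*That laboratory effects will have vanished by Week 16.* A reader might infer this from clinical trial #2 in Section 1. There, the mean IOP rise went from 7 mmHg at Week 12 to 1 "mmHg higher than baseline at 16 weeks, i.e. 4 weeks after DexNP treatment was stopped", and the mean cortisol fall went from 2.5 to 0.4. But IOP is a local ocular measure and cortisol is not in the 6.3 panels. The DexNP arm had been tapered to one drop a day by weeks 9–12. The Week 12 cortisol change is itself uncertain: if the ± value of 4.5 is an SD and all 12 patients were measured, the 95% interval is 2.5 ± 2.201 × 4.5/√12, or −0.4 to 5.4. HbA1c, the listed analyte for which that trial is reported, is described as unaffected. Nothing shows a listed analyte changing on DexNP, let alone recovering.

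*That cortisol should be added to the panel.* The protocol's own reading is "Serum cortisol was mildly affected by both treatments". That trial had no vehicle arm, mean cortisol already differed between arms at baseline (9.7 versus 14.2), and neither units nor sampling time is given. Adding the assay would be a preference, not a correction.

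**Conclusion.** Wrong as written. Section 6.3 and Appendix 1 give incompatible times for the sole planned post-baseline laboratory sample, and the protocol does not say which applies. A site working from Appendix 1 collects no scheduled on-treatment laboratory data, and its post-baseline sample is taken 22 to 34 days off drug. For a named safety endpoint, the number of scheduled on-treatment samples is up to 96 under one text and none under the other.

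The case rests on a simple ground: a trial whose objective is to monitor safety during 12 weeks of treatment needs its laboratory endpoint measured on treatment. It does not depend on any belief about which analytes would move or recover.

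The assumptions are that the last drop is taken at the Week 12 visit and that the table columns are as printed, which the neighbouring rows support. How many sites would follow Appendix 1 cannot be known from the documents. The screening-versus-baseline wording is minor and is covered by 10.6.1. The primary efficacy analysis is unaffected.

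**What to change.** 1. In Appendix 1, mark the blood test at Visit 6 (Week 12). Keep the Visit 1 mark, which the HbA1c and eGFR eligibility checks require.
2. In Section 6.3, state that the Visit 1 sample is the laboratory baseline, in line with 10.6.1. The Visit 1 draw must then cover the full panel listed in 6.3.
3. Decide on Week 16. Either delete its mark from Appendix 1, or keep it as an off-drug recovery sample and add it to 6.3 so that the two texts agree.

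The edits are confined to one row of Appendix 1 and the timing sentence of 6.3. Section 10.6.5 can stay as it is, since it already summarises laboratory data by visit. If Week 16 is deleted, sites using Appendix 1 move one draw per patient from Week 16 to Week 12, with no increase in number. If Week 16 is kept, up to 96 draws are added, one per randomised patient.
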